# Aims

To compare the effectiveness of 7.0 mm-wide diameter implants with 5.0 mmconventional diameter implants placed immediately after tooth extraction in the molar region.

Test hypothesis: there is no difference in clinical outcomes between the two procedures, against the alternative hypothesis of a difference.

# Study Design

Multicenter randomized controlled trial (RCT) of parallel group design. Each patient will provide only one implant-supported crown. For patients with multiple teeth to be extracted, the operator will be free, at the screening visit, to select the tooth to be included in the trial. The trial will have a duration of 5 years post-loading.

- Randomisation: using computer generated random numbers, centralized with sequentially sealed opaque envelopes provided by the study adviser.
- Allocation concealment: operators will know about the intervention to be delivered by opening a sealed envelope after the tooth has been extracted.
- Blinding: independent and blind assessors at each centre will assess implant stability. Bone level changes and aesthetic evaluation will be done by a single blinded and independent assessor who will evaluate the outcomes of all centers.

The principles outlined in the Declaration of Helsinki on clinical research involving human subjects will be adhered to. A written informed consent will be obtained for each patient.

The trial will be reported according to the CONSORT statement for improving the quality of reports of parallel-group randomized trials (http://www.consort-statement.org/).

# Inclusion criteria

Any patient requiring at least one single immediate post-extractive implant in the posterior jaw (molar areas only), being at least 18 year old and able to sign an informed consent. There must be sufficient bone to allow the placement of an implant at least a 7 mm-wide and 7 mm-long.

Preoperative radiographs have to be taken. Investigators are free to choose the most appropriate examination according to the clinical case (intra-oral, panoramic, CT scans, etc.).

Patients will be grouped into: 1) non smokers; 2) moderate smokers (up to 10 cigarettes/day); 3) heavy smokers (more than 10 cigarettes/day), according to what they declare.

### **Exclusion criteria**

- General contraindications to implant surgery.
- Immunosuppressed or immunocompromised patients.
- Patients irradiated in the head and/or neck.
- Uncontrolled diabetes.
- Pregnancy or lactation.
- Active periodontal disease.
- Poor oral hygiene and motivation.
- Addiction to alcohol or drugs.
- Psychiatric problems.
- Patients with an acute infection (abscess) in the site intended for implant placement.
- Necessity to lift the maxillary sinus.
- Patients unable to commit to a 5-year follow-up.
- Patients treated or under treatment with intravenous amino-bisphosphonates.
- Lack of bony walls surrounding the future implant.

- Patients participating in other studies, if the present protocol could not be fully adhered to. In case of doubts please contact the study coordinator.

### Study population and number of patients to be included

Prior to enrollment, all patients will be asked to read and if they understood it, to sign an informed consent form to document that they understand the scope of the study (including procedures, follow-up evaluations, and any potential risks involved), were allowed to ask questions pertaining to this study, and were apprised of treatment alternatives. The study is open to qualifying patients without regard to sex or race. Seventy patients will be included, 35 in each group, each center treating 10 patients each.

#### Outcome measures

**Crown failure:** whether it will not be possible to place the crown because of implant failure or secondary to implant failure, or crown that has to be remade for any reason.

**Implant failure**: Implant failure is defined as implant mobility and/or any infection dictating implant removal, and or/any mechanical problems rendering the implant unusable. The stability of each individual implant will be measured by the independent and blinded outcome assessor manually with a reverse torque of 20 Ncm at abutment connection and at delivery of the definitive crown, or by assessing the

stability of the crown, using the handles of two metallic instruments, at 1 and 5 years after loading.

**Biological and biomechanical complications**: will be recorded and reported by study group. Examples of biological complications are: fistula, peri-implantitis. Examples of biomechanical complications are fracture of the metal screws, loosening of the crown, fracture of ceramic.

**Peri-implant marginal bone level changes**: digital intraoral periapical radiographs will be made with the paralleling technique at implant placement, implant loading, 1 and 5 years after loading. In case of unreadable radiograph, the radiograph has to be made again. Radiographs will be converted to TIFF format with a 600 dpi resolution, and stored in a personal computer. Peri-implant marginal bone levels will be measured using the Scion Image (Scion Corporation, Frederick, MD, USA) software. The software will be calibrated for every single image using the known implant length or the diameter of the implant collar. Measurements of the mesial and distal bone crest level adjacent to each implant will be made to the nearest 0.01 mm. Reference points for the linear measurements will be: the coronal margin of the implant collar and the most coronal point of bone-to-implant contact. Bone levels will be measured at both mesial and distal sides and averaged. Bone level at single implants will be averaged at group level.

Aesthetic evaluation of the clinical pictures, taken at delivery of the final restorations, 1 and 5 years follow-ups, on a computer screen by an independent blinded dentist. The pictures of the vestibular and occlusal aspects have to include the 2 adjacent teeth, when present. The aesthetic evaluation will be done following the pink aesthetic score(1).

**Patient satisfaction**: At the delivery of the final restorations, 1 and 5 years follow-up the independent outcome assessor at each centre will ask to the patient the following questions:

1) Are you satisfied with the function of your implant supported tooth? Possible answers: yes absolutely, yes partly, not sure, not really, absolutely not.

2) Are you satisfied with the aesthetic outcome of your implant supported tooth? Possible answers: yes absolutely, yes partly, not sure, not really, absolutely not.

3) Would you undergo the same therapy again? Possible answers: "yes" or "no".

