### 1 year after loading (APPENDIX 3):

- Crowns will be manually tested for stability.

- Periapical radiographs and clinical pictures of the study implants have to be taken.

- The satisfaction questionnaire has to be filled in.

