### Time

Day 1	extraction/inclusion & allocation/implant placement/photos/rx
Week 1	post-op control
Month 1	post-op control
Month 4	implant stability/impression
Within 1 month	implant stability/definitive/rx/photos/questionnaire
1 year postloading	implant stability/rx/photos/questionnaire
5 years postloading	implant stability/rx/photos/questionnaire

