# Drop-outs

All drop-outs should be reported and the reason for dropping out should be investigated and reported per study group in APPENDIX 4. None of the included patient can be excluded for any reasons by the clinical investigators.

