### Statistical analysis

All data analysis will be carried out according to a pre-established analysis plan by a biostatistician with expertise in dentistry blinded to group allocation. A comparison of the baseline characteristics between groups will be presented. Differences in the proportion of crown/implant failures and other complications will be compared

between the groups using a chi-square test. Means of continuous variables (marginal bone level changes, aesthetic scores) will be compared using an independent sample t-test. Comparisons between, 1 and 5 years with the baseline measurements will be made by paired tests to detect any changes in marginal bone level changes for each study group with the baseline value as a covariate. All statistical comparisons will be conducted at the 0.05 level of significance.

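### Patients who lose the implant before loading have no scheduled satisfaction contact, so question 3 is collected only from those who reach a crown

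*Protocol*

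**What the plan says.** Under Outcome measures (Patient satisfaction) the Protocol states: "At the delivery of the final restorations, 1 and 5 years follow-up the independent outcome assessor at each centre will ask to the patient the" three questions. Questions 1 and 2 are about the function and the look of an existing restoration, for example "Are you satisfied with the function of your implant supported tooth". Question 3 is "Would you undergo the same therapy again", answered yes or no.

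That sentence does not say from when the years are counted. The headings of the two late visits do: both run from loading. So does the Time table, where the first late visit reads "1 year postloading implant stability/rx/photos/questionnaire". Study Design likewise counts the trial's duration from loading.

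Inclusion and allocation happen earlier, on the day of extraction (Operative procedures; Time). The definition of crown failure foresees that some patients will never get a crown because the implant failed first. The Drop-outs section keeps such patients in: "None of the included patient can be excluded for any reasons by the clinical investigators".

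**The concern.** The questionnaire hangs on an event, delivery of the crown, that not every randomised patient reaches. Bone level and the aesthetic score cannot be measured on a lost implant, so their absence is unavoidable. Question 3 is different: a patient who lost the implant can still say whether they would go through the treatment again, and is among those whose answer is most informative. If the schedule is followed as written, that answer is not asked for.

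Question 3 would then be compared between subsets defined by survival to loading, which the implant diameter may itself affect. An analysis plan can say how to treat missing answers, but it cannot recover answers that nobody collected. When the question is asked, and of whom, has to be settled in the protocol and its follow-up forms.

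**Working it through.** **Step 1. Follow a patient whose implant is lost in the healing period.**

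- Day 1: included and allocated (Time).
- Loss during healing: counted as an implant failure and, because no crown can be placed, as a crown failure (Outcome measures). Radiographs, pictures and the complications form are required (final paragraphs of the 5-year visit section). No questionnaire is attached.
- Crown delivery: does not take place, so the first questionnaire has no occasion.
- 1 and 5 years after loading: there is no loading date to count from.
- 6-monthly recalls: these cover all patients, but for maintenance only.
- Status: still in the trial (Drop-outs).

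The section on the visit four months after placement also lists the questionnaire. That section runs on to crown delivery within a further month, and both the Patient satisfaction text and the Time table put the questionnaire at delivery. Even if the four-month listing were taken literally, it would supply one contact and leave the 1- and 5-year contacts undefined.

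**Step 2. Size, by illustration.**

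From the Protocol: "Seventy patients will be included, 35 in each group, each center treating 10 patients each", so n = 35 per arm. The Protocol gives no early failure rate and no expected answers to question 3. The following are therefore assumptions:

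- s = 0.90 of patients with a loaded crown answer yes, in both arms.
- Every early loss would answer no.
- Early losses are a in one arm and b in the other.

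As scheduled, only crowned patients answer, so both arms show 90% and the difference is 0 whatever a and b are. Over all randomised patients, the proportion answering yes is s(35 − a)/35 in one arm and s(35 − b)/35 in the other, and the difference is s(b − a)/35.

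| Losses a v b | Shown as scheduled | All randomised | Difference (points) | Not asked |
|---|---|---|---|---|
| 1 v 1 | 90% v 90% | 30.6/35 = 87.4% v 87.4% | 0 | 2/70 = 2.9% |
| 1 v 3 | 90% v 90% | 87.4% v 28.8/35 = 82.3% | 0.9 × 2/35 = 5.1 | 4/70 = 5.7% |
| 1 v 5 | 90% v 90% | 87.4% v 27.0/35 = 77.1% | 0.9 × 4/35 = 10.3 | 6/70 = 8.6% |
| 0 v 5 | 90% v 90% | 31.5/35 = 90.0% v 77.1% | 0.9 × 5/35 = 12.9 | 5/70 = 7.1% |

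**Step 3. How far this depends on the all-no assumption.**

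If a fraction q of early losses would answer yes, the difference becomes (0.90 − q)(b − a)/35. At q = 0 it gives the table. At q = 0.45 each difference is halved. At q = 0.90 it vanishes. The gap therefore needs two things: unequal losses, and less favourable answers from those who lost the implant. With equal losses only the second is needed for both arms to be overstated.

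**Step 4. Times that match those of crowned patients.**

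Counted from placement, with delivery at the end of the one-month window: delivery 4 + 1 = 5 months; 1 year after loading 5 + 12 = 17 months; 5 years after loading 5 + 60 = 65 months. This takes loading to be delivery of the definitive crown, since no earlier crown is described.

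**The case against.** The strongest reply is that the harm is already visible. An implant lost before loading counts as an implant failure and as a crown failure, and the Statistical analysis section compares both between groups. That stands: the failure outcomes are not affected. It does not repair question 3, which is a separate listed outcome and would be reported from survivors only.

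A second reply is that little can be recovered. Questions 1 and 2 presuppose an implant-supported tooth, which these patients do not have. That also stands. What can be recovered is one yes/no item in a few patients.

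Third, all the inputs on answers and losses are assumed. That is so, and no p-value is attached to them. The section sets a general threshold ("All statistical comparisons will be conducted at the 0.05 level of significance") but names no test for satisfaction, and with counts this small significance would turn on the choice of test.

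A reader might also infer more than the text supports:

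- **That every visit after healing is timed from loading.** The four-month visit is timed from placement, and the 6-monthly recalls cover all patients with no loading anchor stated.
- **That a replacement implant would restart the clock and bring its answers into the randomised arm.** The Protocol never mentions replacement, and its instructions on radiographs and pictures refer to the study implants. All that can be said is that the handling is not stated.
- **That these patients are barred from follow-up.** Nothing forbids asking them. The schedule simply gives no occasion to do so.

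**Conclusion.** The gap is real but narrow. All scheduled questionnaire contacts depend on crown delivery or loading, while the Protocol foresees patients who never get that far and keeps them in the trial. Question 3, which they could answer, is therefore scheduled only for patients selected by an event after randomisation.

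Under the assumptions above, the hidden difference runs from 0 with equal losses to 12.9 points with 0 v 5. The Protocol gives no figure that would place the trial within that range. If there are no early losses, nothing is lost.

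Severity is minor: one item, few patients, and losses that already count as failures. It is still worth correcting, because the missing answers cannot be obtained afterwards.

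**What to change.** In Outcome measures (Patient satisfaction), the 1-year and 5-year visit sections and the Time table, add:

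- Patients without a loaded study crown are asked question 3, about the originally allocated treatment, at about 5, 17 and 65 months after implant placement, for example at the nearest 6-monthly recall.
- For these patients questions 1 and 2 are recorded as not applicable.
- Answers about any non-study implant are not counted as answers for the allocated one.
- Question 3 is reported for all randomised patients, by group.

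The cost is a few lines in the schedule, one instruction on the follow-up form (Appendix 3), and a few extra questionnaire contacts with patients who are due for recall anyway. Treatment does not change.

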# Materials

Implant type: IB-T (ACH Medical, Gyeonggi-do, South Korea) tapered self-tapping implants, with an internal conical (11° per side) connection, a sand blasted, large grit,

acid-etched surface, and body diameters of 5.0 or 7.0 mm. Operators are free to choose implant lengths (7.0, 8.0, 9.5 and 11.0 mm) according to clinical indications.

Bone substitute: resorbable powder of non-collagenated trabecular bovine bone, having a granulometry of 0.2-1.0 mm (S1, MedPark, Busan, South Korea) and has to be hydrated with physiologic solution to become sticky.

Definitive crowns: Screw-retained zirconia crowns.

# **Clinical procedures**

### Screening visit (APPENDIX 1)

Potentially eligible patients are screened to establish their eligibility for the study. Please complete APPENDIX 1 (Patient eligibility CRF) and record the number and reason of non-included patients. Patients must be informed on the nature of the study and must sign an informed consent, if they understood the scope of the study and agreed to participate. A preoperative radiograph must be obtained for every included patient.

After determining that the patient is qualified for the study, and informed consent has been given, a thorough oral examination will be performed to assess health status, identify oral pathologies that require treatment prior to implant therapy, and analyze available bone over vital structures and adjacent to remaining natural teeth. Severe caries and periodontal disease will be identified and treated. Implant selection is predicated on the location and anatomic morphology of the proposed implant receptor site and its contiguous structures. Therefore, radiographic examinations will be performed to assist with treatment planning and used as a screening tool to assess the patient's overall dental health. To record a visual baseline, preoperative facial and occlusal digital photographs will be made of each patient intraorally to document the condition of the dental anatomy and state of soft tissue health.

### **OPERATIVE PROCEDURES**

Please complete APPENDIX 2 (Surgical and prosthetic CRF)

**Prophylactic therapy**: Patients will be administered 1 g amoxicillin 3 times a day for 6 days starting the day before tooth extraction. Patients allergic to penicillin will be prescribed clindamycin 300 mg 3 times a day for 6 days starting the day before the intervention.

Patients will rinse with chlorhexidine mouthwash 0.2% for 1 minute prior to the intervention.

Local anaesthesia: Articain with adrenaline 1:100.000.

**Tooth extraction**: Tooth extractions should be performed as atraumatically as possible attempting to preserve the buccal alveolar bone. Extraction sockets have to be carefully cleaned from any remains of granulation tissue. The wider diameter of the socket will be measured with a periodontal probe and reported in mm.

**Disclosure of the randomised allocation**: Once the tooth has been extracted and whether there is sufficient buccal bone, the patient will be finally included in the study and the operator will know whether the patient will receive large or conventional diameter implant by opening a sealed envelope. It is absolutely forbidden to open the envelope containing the randomisation code before. It will be reported in the Surgical and prosthetic CRF (APPENDIX 2) the patient sequential number contained in the envelope and to which group the patient was allocated.

**Implant installation technique**: drills will be used to prepare the implant site as suggested by the manufacturer. The intention is to stabilize the implant in the post-extractive site. Implants will be placed slightly subcrestally, about 1 to 2 mm below the most apical bone peak. The largest residual gap between the bony walls and the implant will be measured with a periodontal probe in mm. Any residual gap between the implant and the socket walls will be filled with granular bone substitute. No other grafting material is allowed.

Healing abutments will be placed and occlusal pictures showing the implants in place will be taken.

A periapical radiograph just after implant placement has to be taken.

Implants will be left to heal non-submerged for 4 months.

# Post-surgical instructions and follow-up:

- Antibiotic prophylaxis previously described.

- Ibuprofen 400 mg will be prescribed, but patients will be instructed not to take it in absence of pain.

- Chlorhexidine mouthwash 0.12% for 1 minute twice a day for 2 weeks.

# Check-ups

- 1 week after tooth extraction, all patients will be recalled and checked. Sutures will be removed.

- 1 month after tooth extraction all patients will be recalled and checked.

# Four months after implant placement:

- Implants will be manually tested for stability.

- Impressions with pick-up or transfer-coping impression copings will be made with a polyether or a poly-vinylsiloxane material.

- Definitive screw-retained zirconia crowns (previously cemented extra-orally) will be delivered within one month.

- Periapical radiographs and clinical pictures of the study implants have to be made.

- The satisfaction questionnaire has to be filled in.

### 1 year after loading (APPENDIX 3):

- Crowns will be manually tested for stability.

- Periapical radiographs and clinical pictures of the study implants have to be taken.

- The satisfaction questionnaire has to be filled in.

### 5 years after loading (APPENDIX 3):

- Crowns will be manually tested for stability.

- Periapical radiographs and clinical pictures of the study implants have to be taken.

- The satisfaction questionnaire has to be filled in.

All patients will be recalled every 6 months for professional maintenance.

In case of suspected implant loss, peri-implantitis, fistula, etc., observed during any of the scheduled visit or during an emergency visit, intraoral radiographs and clinical pictures have to be taken and the "Complications, protocol deviation and drop-out CRF" (APPENDIX 4) should be filled in.

### Time

Day 1	extraction/inclusion & allocation/implant placement/photos/rx
Week 1	post-op control
Month 1	post-op control
Month 4	implant stability/impression
Within 1 month	implant stability/definitive/rx/photos/questionnaire
1 year postloading	implant stability/rx/photos/questionnaire
5 years postloading	implant stability/rx/photos/questionnaire

# Drop-outs

All drop-outs should be reported and the reason for dropping out should be investigated and reported per study group in APPENDIX 4. None of the included patient can be excluded for any reasons by the clinical investigators.

### Statistical analysis

All data analysis will be carried out according to a pre-established analysis plan by a biostatistician with expertise in dentistry blinded to group allocation. A comparison of the baseline characteristics between groups will be presented. Differences in the proportion of crown/implant failures and other complications will be compared

between the groups using a chi-square test. Means of continuous variables (marginal bone level changes, aesthetic scores) will be compared using an independent sample t-test. Comparisons between, 1 and 5 years with the baseline measurements will be made by paired tests to detect any changes in marginal bone level changes for each study group with the baseline value as a covariate. All statistical comparisons will be conducted at the 0.05 level of significance.

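### Does leaving the version of the chi-square test unstated, with 35 patients per arm, call for a named exact test?

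*Protocol*

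**What the plan says.** Under Statistical analysis, the protocol gives one method for all binary outcomes: "Differences in the proportion of crown/implant failures and other complications will be compared" "between the groups using a chi-square test". The same section sets the threshold: "All statistical comparisons will be conducted at the 0.05 level of significance". It names no continuity correction, no exact test and no rule for small counts. It opens, however, by placing all analysis under an analysis plan fixed in advance and carried out by a biostatistician who does not know the allocation. That plan is not at hand.

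The size of the comparison comes from two other sections. Study population and number of patients to be included states: "Seventy patients will be included, 35 in each group, each center treating 10 patients each". Study Design states: "Each patient will provide only one implant-supported crown". Each arm therefore contributes at most 35 independent yes/no results. The Aims section sets a non-directional alternative, so the tests are two-sided.

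No expected failure rate is given. Outcome measures defines crown failure broadly; it includes a "crown that has to be remade for any reason".

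**The concern.** The chi-square test is a large-sample approximation, and failures may be few. With equal arms, the expected number of failures per arm is half the total, so it stays below the conventional value of 5 unless at least 10 of the 70 patients fail. The name also covers more than one calculation. The uncorrected Pearson test and the Yates-corrected test can fall on opposite sides of 0.05 for the same table, and a report of either would comply with the protocol.

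What would be at stake is the verdict on crown and implant failure, the first two outcomes listed. Results are due for publication at 1 and 5 years after loading, so the two reports could even use different versions without breaching the text. The natural remedy would be to replace the chi-square test with one named exact test.

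**Working it through.** **Inputs.** 35 per arm (Study population), one crown per patient (Study Design), two-sided testing (Aims), level 0.05 (Statistical analysis). The protocol gives no event rate, effect size or power, so it has no figure of its own to reproduce. All rates below are assumptions.

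**Formulas.** Let the arms have *a* and *b* failures, *s* = *a* + *b* and *d* = |*a* − *b*|. At 35 v 35 the statistics reduce to:

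- Pearson, uncorrected: 70*d*² / [*s*(70 − *s*)]
- Yates, corrected: 70(*d* − 1)² / [*s*(70 − *s*)]

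Both are compared with 3.84 (chi-square, 1 degree of freedom).

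Example, 4 v 0: Pearson = 70 × 16 / (4 × 66) = 4.24, p = 0.039. Yates = 70 × 9 / (4 × 66) = 2.39, p = 0.122.

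**Step 1: where the versions split.**

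| Failures | Expected per arm | Pearson p | Yates p | Fisher p |
|---|---|---|---|---|
| 4 v 0 | 2.0 | 0.039 | 0.122 | 0.114 |
| 5 v 0 | 2.5 | 0.020 | 0.063 | 0.054 |
| 6 v 1 | 3.5 | 0.046 | 0.111 | 0.106 |
| 7 v 1 | 4.0 | 0.024 | 0.060 | 0.055 |
| 8 v 2 | 5.0 | 0.040 | 0.088 | 0.084 |
| 13 v 5 | 9.0 | 0.029 | 0.056 | 0.054 |
| 16 v 8 | 12.0 | 0.044 | 0.078 | 0.077 |
| 22 v 13 | 17.5 | 0.031 | 0.056 | 0.055 |

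The last three rows have expected counts well above 5. The split is therefore a general property of the continuity correction at this sample size and is not caused by sparse data. Clearer results do not depend on the version: 6 v 0 gives 0.010, 0.033 and 0.025, and 8 v 1 gives 0.012, 0.032 and 0.028.

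**Step 2: does the uncorrected test hold its level?** Sum the binomial probabilities of all 36 × 36 tables that it rejects, with the same rate in both arms.

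| Common rate | True size, Pearson | True size, Yates or Fisher | Chance the version changes the verdict |
|---|---|---|---|
| 1% | 0.06% | 0.0% | 0.06% |
| 2% | 0.5% | 0.01% | 0.5% |
| 3% | 1.4% | 0.04% | 1.4% |
| 5% | 3.6% | 0.3% | 3.4% |
| 10% | 5.7% | 1.3% | 4.4% |
| 15% | 5.3% | 2.2% | 3.1% |

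The maximum over all common rates is 5.7% for Pearson (near a rate of 10%) and 2.9% for Yates and Fisher.

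**Step 3: what an exact test would cost.**

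| True rates | Pearson power | Boschloo power | Fisher power | Yates power |
|---|---|---|---|---|
| 5% v 20% | 0.52 | 0.41 | 0.33 | 0.33 |
| 5% v 30% | 0.84 | 0.80 | 0.74 | 0.74 |

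Exact tests also disagree with each other: 5 v 0 gives 0.034 by Boschloo and 0.054 by Fisher.

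**Step 4: is Yates simply Fisher under another name?** At 35 v 35 the two give the same 0.05 verdict in every table. At 34 v 35 they differ in 28 tables, and at 33 v 35 in 26. Over 5 years of follow-up, exactly equal arms at analysis cannot be assumed.

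**The case for a change.** The strongest case for a change is that the protocol was not silent. It chose a test, so it can be judged on that choice. If the arms truly differ, the version matters more than the null figures suggest: the chance that corrected and uncorrected tests disagree is 19% at 5% v 20%, 21% at 2% v 10% and 25% at 3% v 15%. A likelihood-ratio test is also a chi-square test, and its true size reaches 9.0% at 35 v 35. One sentence would remove all of this.

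The ambiguity stands, and so does the benefit of settling the version before the data are unblinded. Three parts of the case do not carry it further.

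- The disagreement under a true difference is the power gap between the two versions seen from another side. At 5% v 20% it is 0.52 − 0.33 = 0.19. It measures a trade-off between power and conservatism and does not show that either version is wrong. It also needs a four- to fivefold difference in rates that the protocol nowhere assumes.
- An unqualified chi-square comparison of proportions ordinarily means Pearson's test. The likelihood-ratio reading is possible but unusual.
- An exact test is not the only way to fix the version. Stating that Pearson's test is used without correction would do so with no loss of power, at the price of a size up to 5.7%. Preferring Boschloo or Fisher is a matter of judgement.

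**Conclusion.** The concern does not call for a change to the protocol. The protocol names a usual test for two proportions. Read in the ordinary way, that test roughly keeps its 5% level at 35 per arm: at most 5.7%, and below 5% when failures are rare. What is left open is whether a continuity correction applies. A protocol commonly leaves that to its analysis plan, and a biostatistician blinded to allocation has little means of choosing the version to favour one implant.

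The effect is confined to borderline tables. With no true difference, the choice of version changes the verdict in 0.06% to 4.4% of trials for common rates of 1% to 15%. An exact test would guarantee the level but lower the power of a 70-patient trial, so it is a fair trade-off and not a correction of an error.

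The conclusion rests on assumed failure rates, on arms of 35 at analysis, and on reading the named test as Pearson's. If the analysis plan also leaves the version open, one line there, written before unblinding, is enough.

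### Does testing bone level change from a film taken after the allocated implant is in place make the between-arm comparison unsound?

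*Protocol*

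**What the plan says.** The Protocol lists peri-implant marginal bone level change as an outcome. Under Outcome measures, "digital intraoral periapical radiographs will be made with the paralleling technique at implant placement, implant loading, 1 and 5 years after loading". Level is a distance on the film: "Reference points for the linear measurements will be: the coronal margin of the implant collar and the most coronal point of bone-to-implant contact". Mesial and distal readings are averaged for each implant, and then "Bone level at single implants will be averaged at group level".

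The Statistical analysis section gives the between-arm test: "Means of continuous variables (marginal bone level changes, aesthetic scores) will be compared using an independent sample t-test". The paired tests against baseline in the same section are run within each group, and the baseline covariate is attached to those. The section also says: "A comparison of the baseline characteristics between groups will be presented". It refers to a pre-established analysis plan, which is not at hand.

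Under Operative procedures, the envelope is opened after extraction, the implant is then placed, and the first film follows. Collars are to sit 1 to 2 mm subcrestally, gaps between implant and socket are filled with bone substitute, and "The largest residual gap between the bony walls and the implant will be measured with a periodontal probe in mm". The implants have an "acid-etched surface, and body diameters of 5.0 or 7.0 mm". Healing takes 4 months, after which crowns "will be delivered within one month".

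**The concern.** A change score is easiest to interpret when its baseline was recorded before allocation, because randomisation then makes the expected baselines equal. Here that is impossible. Level is measured from the implant collar, so it does not exist until the allocated implant is in the jaw. Both candidate baselines, placement and loading, come after allocation.

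The treatment itself might also move the starting level. A narrower implant in the same socket leaves a wider gap, and level is read at bone contact. If the arms start at different levels, a difference in change could reflect the start and not the end, and equal changes could hide a difference that was there from the first film. In addition, the analysis section does not say which film is the baseline, and a loading baseline would leave out whatever happens during healing. A reader of the 1-year or 5-year report might then draw the wrong conclusion about which implant leaves more bone.

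**Working it through.** **Inputs from the Protocol.** 35 patients per arm; significance level 0.05, taken as two-sided because the alternative is a difference in either direction; diameters 5.0 and 7.0 mm; loading 4 to 5 months after placement; films at placement, loading, 1 and 5 years after loading. The Protocol gives no SD, correlation or expected difference for bone level, so those below are assumptions. It states no figure on this point to reproduce.

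**1. The identity.** Difference in change = difference in final level − difference in starting level. This is algebra and holds for every change score in every trial.

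In 10,000 simulated trials per case, with 35 per arm, level SD 1 and start-to-final correlation 0.5:

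| Start difference (SD) | Final difference (SD) | Mean difference in change | Change test rejects | Final-level test rejects |
|---|---|---|---|---|
| 0 | 0 | 0.00 | 5% | 5% |
| 0 | 0.5 | 0.50 | 55% | 55% |
| −0.5 | 0 | 0.50 | 55% | 5% |
| 0.5 | 0.5 | 0.00 | 5% | 54% |

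The change test answers its own question correctly in every row: it rejects at 5% when the mean changes are equal and more often when they differ. It differs from the level test only where a starting difference is put in.

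**2. Does the Protocol imply a starting difference?** In a socket at least 7 mm wide with a centred implant, the extra gap per side is (7.0 − 5.0)/2 = 1.0 mm. That distance is horizontal. Bone level is read along the implant, from collar to first contact, and the gap is filled with graft. How a filled horizontal gap appears as a vertical reading is not stated, so size and direction are unknown. If contact is at the collar in both arms at placement, both starting levels are 0, and change from placement equals final level.

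**3. How large could the effect be?** Suppose final levels are equal and the arms start *d* mm apart. The test statistic is non-central t with 68 df and non-centrality *d*/(SD × √(2/35)), where √(2/35) = 0.239. For *d* = 0.2 and SD = 0.6, that is 0.2/(0.6 × 0.239) = 1.39, which gives 28%.

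| *d* (mm) | SD of change 0.6 | 1.0 | 1.5 |
|---|---|---|---|
| 0.1 | 11% | 7% | 6% |
| 0.2 | 28% | 13% | 8.5% |
| 0.3 | 54% | 24% | 13% |

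In these cases the mean changes really do differ by *d*, so for change the rejections are correct. They become errors only if the result is reported as a difference in final level.

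**4. Would a test of level escape the problem?** No. Depth is set by the operator after allocation, within a stated range of 1 to 2 mm. If bone height is equal but mean depth differs by *d* and shifts the reading by the same amount, the formula in step 3 gives the same table, with the SD of level in place of the SD of change.

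Running both tests also has a cost. With no true difference and a start-to-final correlation of 0.3/0.5/0.7, the chance that at least one is significant at a single time point is 8.8/9.1/9.4%.

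**5. What would a loading baseline leave out?** For the 1-year film, 4/16 = 25% to 5/17 = 29% of the time since placement; for the 5-year film, 4/64 = 6% to 5/65 = 8%. These are shares of calendar time, not of bone change or of an arm effect. A loading baseline defines a post-loading outcome, and the comparison of that outcome is still valid.

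**The case for a change.** The strongest case for the concern is this. Randomisation does not guarantee equal starting levels, because no level precedes allocation. Diameter, bone contact and operator-set depth make a starting difference conceivable. The only stated between-arm test cannot tell a starting difference from a final one. The baseline film is unnamed, so it could be chosen after the data are seen. A supportive comparison of level would need no new film.

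The facts in this stand: the order of events, the algebra, and the unnamed film. The conclusion does not follow from them. That a test cannot answer a question it was not set is no fault in the test. The starting difference is conceivable but not shown. Group averages of bone level are planned, and if they are reported for each film, readers can see where the arms began and ended; what would then be missing is a p-value. The suggested level comparison leaves the stated test and its result unchanged and has a matching weakness, so adding it is a preference between two imperfect measures. Which film is the baseline, and whether placement levels appear in the baseline table, are details an analysis plan commonly settles. The Protocol refers to such a plan, so their absence here is not a defect.

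**Conclusion.** The concern does not hold. The Protocol names change in bone level as the outcome and tests change between randomised groups with a suitable test. With either film as baseline, the result is a sound comparison of change from that film, rejecting in about 5% of trials when allocation has no effect.

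The documents support no figure for bias. The 6% to 54% rejection rates need an assumed starting difference of 0.1 to 0.3 mm, an assumed SD of 0.6 to 1.5 mm, equal final levels, and a reader who takes change to mean final level. The 25% to 29% of time before a loading baseline is a matter of how the outcome is defined.

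This conclusion assumes that results are reported as change, as the Protocol words them, and that the analysis plan names the baseline film.
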